4.5 STUDY DISCONTINUATION

Genentech, Study Center, and the Principal Investigator have the right to terminate this study at any time. Reasons for terminating the study may include the following:

- The incidence or severity of adverse events in this or other studies indicates a potential health hazard to subjects
- Subject enrollment is unsatisfactory. The enrollment time period will start only
 after all procedures and protocol will be IRB approved.
- Data recording are inaccurate or incomplete
- Study protocol not followed

4.6 STATISTICAL METHODS

4.6.1 Analysis of the Conduct of the Study

We will follow IRB guidelines to ensure that all study procedures are conducted appropriately.

The principal investigator will have periodic meetings with all study staff to oversee any possible study deviation or violation to the protocol. We have a step-by-step checklist of the scan session and safety precautions that the research team follows for every subject. We will also ask subjects about their comfort level throughout the session.

[name] or another co-investigator will monitor all MR-PET scanning. [name], the PI, and all other study staff (co-investigators and research technicians) are certified in the Partners Health Care System Human Subject Protection Education Requirements and are familiar with the procedures and steps necessary to report adverse events to the IRB committee

4.6.2 Analysis of Treatment Group Comparability

We will have only one treatment group (Ocrelizumab) in which we will assess neuroinflammation by means of ¹¹C-PBR28 MR-PET imaging (SUVR) at 2 time points: 1) baseline, 2) 12-month follow up.

At baseline, patient SUVR across different regions in WM and gray matter will be compared with brain SUVR data from a healthy control dataset obtained at the Martinos Center by using linear regression models and adjusting for age and PBR affinity. Group comparisons (baseline vs 12-month) will be carried out using region of interest analysis or voxelwise approaches by means of paired-test and/or ANOVA. In patients, regression models will be used to determine the relation between SUVR and structural MRI metrics (lesion load, MTR in NAWM and cortex), and adjusting for age and PBR affinity. Multivariate regression models will be also used to assess the relation between SUVR and EDSS at baseline and EDSS change at 1-year follow up, adjusting for PBR affinity. For evaluating changes/drug effects in the cortex and associations between cortical

SUVR and MRI or clinical metrics we will perform vertex-wise surface-based analyses by sampling SUVR maps at mid-cortical depth to reduce partial volume effects. Age and PBR affinity will be included as covariates of no interest when appropriate.

4.6.3 Efficacy Analysis

Not applicable

4.6.4 Safety Analysis

List all safety endpoints (i.e., endpoints relating to adverse events, laboratory assessments, physical examinations, vital signs, or any special safety assessments). Variables relating to adverse events might include timing, severity, relationship to drug, relationship to therapy, outcome, effect on therapy, and degree of seriousness.

Indicate the subject groups (usually all subjects) to be used in analyzing the safety variables.

Unless specific safety questions have been included in the study objectives (and an appropriate sample size and study design have been established to permit answering those questions), it is usually sufficient to use descriptive procedures for summarizing safety data.

4.6.5 Missing Data

Data analysis will be conducted even in the case of missing data by considering separately each time point. We will consider missing data all the metrics that are not acquired within 3-months of the expected time point.

4.6.6 Determination of Sample Size

Quantification of ¹¹C-PBR28 uptake shows excellent scan-rescan stability.

In 5 healthy controls (2 with high affinity binding, HAB, and 2 with mixed affinity binding, MAB for PBR28) we assessed the 3-month scan-rescan stability of 60-90 minutes¹¹C-

[figure not shown]

Fig. 1. Plots illustrate mean % signal change of test-retest 60-90 minutes ¹¹C-PBR28 SUVR in the fusiform gyrus and in the medial prefrontal cortex in 5 healthy controls that underwent ¹¹C-PBR28 MR-

PBR28 SUVR quantification across all cortical regions sampled at mid-cortical depth (50% depth from pial surface). Results show excellent stability of these measures over time, with mean±SD SUVR testretest % change in all regions tested of 0.1±1.16, and with coefficient of variations (COV) across cortical regions below 10%. An

example of test-retest 60-90 minutes SUVR in the fusiform gyrus and medial prefrontal cortex from 5 healthy subjects is illustrated in **Fig. 1**.

11C-PBR28 uptake. We found an increase in 11C-PBR28 uptake in cortical lesions of ~26% in 13 RRMS and of ~29% in 14 SPMS¹², and a variability in ¹¹C-PBR28 uptake of ~10% among subjects. By assuming a variability among subjects of ~10-20%, we have a 90% power (significance level of 5%) to detect an absolute difference in ¹¹C-PBR28 uptake between MS and HC of ~15%. From scan-rescan changes in ¹¹C-PBR28 uptake around ~1%, we anticipate to have a 90% power to detect at least a 1.5% longitudinal change of values over time.

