- 1. The subject will be asked to void again immediately after the scan and he/she will be counseled on the importance of continuing to drink fluids for several more hours. This will increase urine flow rate, which will help minimize the radiation dose to the bladder wall.
- 2. A detailed information sheet on post PET scan procedures will be given to the subject.

Data acquisition: Subjects will be positioned in the BrainPET scanner and data acquisition may start after an intravenous bolus injection of ¹¹C-PBR28 (~12mCi) to capture the 60-90 minutes after radiotracer administration.

During PET acquisition, the following MR protocols will be simultaneously acquired: 1) standard FLAIR protocols for WMLV estimation; 2) T1 anatomical images for Freesurfer cortical reconstruction and coregistration with MR-PET and 7T data (~7 min); standard MTR protocols (~16 min).

Data analysis: Standardized uptake value (SUV) maps of ¹¹C-PBR28 uptake will be created for 60-90-minute PET frame and resampled at 1.25 mm isotropic voxels, as previously detailed¹². Data in MS and in other neurological disorders show that ¹¹C-PBR28 SUV can substitute for, and may even be more sensitive than absolute quantitation^{12, 16, 17}. This method is expected to improve subject tolerability by allowing shorter scan time and not requiring arterial catheterization. In addition, the method allows smaller sample sizes for comparable statistical significance because of the relatively low variability of SUV. Scan-rescan reproducibility data in 5 healthy subjects at our Center demonstrate that quantification of ¹¹C-PBR28 SUV normalized by a reference region (SUVR) has excellent stability over time, with mean±SD SUVR test-retest % change in all regions tested of 0.1±1.16, and with coefficient of variations across brain regions below 10%.

Using a surface-based analysis, all subjects in this study will have acquired 3T anatomical and MTR maps to estimate intracortical MTR at 50% depth from the pial surface. With those 3T maps, specifically the relationship between the extent of microglia and/or macrophages activation and changes in MTR will be investigated. Decreases in MTR would suggest a reduction in cortical myelin content. Furthermore, this study will include whether changes in MTR in WM lesions or normal appearing WM (NAWM) is accompanied by changes in microglia/macrophages activation as measured by ¹¹C-PBR28 MR-PET or whether these processes are unrelated.

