3.3.1 Primary Outcome Measure

¹¹C-PBR28 uptake measured as standardized uptake values (SUV, mean radioactivity/injected dose/weight) from the 60-90 minutes post-injection data) and normalized by a pseudoreference region (SUVR) as previously detailed. Tracer uptake will be assessed in 1) cortex; 2) WM lesions; 3) NAWM.

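### Neither 90% power in section 4.6.6 is supported as stated: the 1.5% longitudinal figure uses only rescan noise in healthy controls, and the 15% MS-versus-control figure needs about 92 controls (two-sided) at the top of its SD range

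*Combined protocol and SAP*

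**What the plan says.** Section 4.6.6 makes two power statements for a study of 24 patients.

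- **Longitudinal change.** It reports 3-month scan-rescan data in 5 healthy controls, with a mean±SD test-retest change of 0.1±1.16%. From "uptake around ~1%, we anticipate to have a 90% power" it goes straight to the conclusion: "we anticipate to have a 90% power to detect at least a 1.5% longitudinal change of values over time".
- **MS versus healthy controls.** "By assuming a variability among subjects of ~10-20%, we have a 90% power (significance level of 5%) to detect an absolute difference in" tracer uptake of about 15%. The observed variability quoted just before is about 10%.

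Section 4.6.2 describes the analyses that these powers serve. For the longitudinal question: "Group comparisons (baseline vs 12-month) will be carried out using region of interest analysis or voxelwise approaches by means of paired-test and/or ANOVA". For the control comparison, baseline SUVR in patients is to be "compared with brain SUVR data from a healthy control dataset obtained at the Martinos Center", by regression adjusted for age and PBR affinity. The size of that dataset is not given.

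Section 3.3.1 defines the primary measure by region: "Tracer uptake will be assessed in 1) cortex; 2) WM lesions; 3) NAWM".

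Section 4.6.6 describes the rescan data as "PBR28 SUVR quantification across all cortical regions sampled at mid-cortical depth". Section 3.1 gives the same 0.1±1.16, but "with coefficient of variations across brain regions below 10"%. Neither says whether 1.16 is an SD across subjects or across regions.

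**The concern.** The denominator of a paired test is the SD of the individual changes. In treated patients over 12 months it has at least two parts: measurement noise, and real differences between patients in how much uptake changes. Rescanning stable, untreated controls after 3 months estimates the first part only. Healthy controls also cannot supply any value for MS white matter lesions, one of the three primary regions.

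The control comparison has a different fault. One power is claimed over a twofold range of SD, which is a fourfold range of variance, without the number of controls that fixes the answer.

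Section 4.6.6 is the only quantitative support for 24 patients, and its longitudinal sentence is the only one that addresses the primary objective. A reader will take 1.5% as the sensitivity of the study and may read a small or null 12-month result as excluding changes that the study could not reliably detect.

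**Working it through.** **Inputs from the protocol.** 24 patients; change of 1.5%; rescan SD of 1.16% (section 4.6.6 rounds the rescan change to about 1%); MS-versus-control difference of 15% with SD 10-20%; significance level 5%; power 90%.

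**Assumptions made here.** Two-sided tests; SDs of 12-month change of 2%, 3%, 5% and 10%; 20 complete pairs as an alternative to 24, since no dropout rate is given; 24 controls where a number is needed; no covariate adjustment.

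**1. Longitudinal, on the plan's own input.** Power of the paired t-test comes from the noncentral t with n−1 degrees of freedom and noncentrality (change/SD)×√n. With n = 24 and SD 1.16%, the noncentrality is (1.5/1.16)×√24 = 6.33 and power is above 99.9%. The change detectable with 90% power is 0.691 SD, so 0.691×1.16 = 0.80%. On the rescan SD alone the claim is more than met.

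**2. How large the SD of change may be.** The change detectable with 90% power is 0.691 SD with 24 pairs and 0.764 SD with 20. The largest SD at which 1.5% still has 90% power is therefore:

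- 24 pairs: 1.5/0.691 = 2.17%
- 20 pairs: 1.5/0.764 = 1.96%

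If 1.16% is the subject-level noise SD and adds independently to true change, the room left for between-patient SD of true change is:

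- 24 pairs: √(2.17² − 1.16²) = 1.83%
- 20 pairs: √(1.96² − 1.16²) = 1.58%

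**3. Range over assumed SDs of 12-month change.**

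| Assumed SD | Power for 1.5%, 24 pairs | Power for 1.5%, 20 pairs | Detectable change, 24 pairs | Detectable change, 20 pairs |
|---|---|---|---|---|
| 2% | 94% | 89% | 1.4% | 1.5% |
| 3% | 65% | 56% | 2.1% | 2.3% |
| 5% | 29% | 25% | 3.5% | 3.8% |
| 10% | 11% | 10% | 6.9% | 7.6% |

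**4. MS versus controls.** For the two-sample t-test with 24 patients and m controls, the noncentrality is 15/(SD×√(1/24 + 1/m)) with 24 + m − 2 degrees of freedom. The smallest m giving 90% power is:

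| SD | Controls needed (two-sided) |
|---|---|
| 10% | 7 |
| 15% | 21 |
| 18% | 45 |
| 20% | 92 |

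At SD 20% a one-sided test needs 45. With an assumed 24 controls, two-sided power for 15% is 99.9% at SD 10%, 92% at SD 15% and 72% at SD 20%. With those 24 controls, 90% power holds up to SD 15.7%, and the detectable difference at SD 20% is 19.1%.

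**The case against.** The best defence of the longitudinal figure is its margin. On the rescan SD the study could detect 0.80%, and the plan states 1.5%, nearly twice that. The claim tolerates an SD of change about 1.9 times the rescan SD (2.17/1.16). The section also discloses that its data come from 5 healthy controls over 3 months. The larger SDs tabulated above are illustrative: if the SD at each scan is about 10%, an SD of change of 10% implies a within-patient correlation of only 0.5, and nothing in the documents points there. This stands as far as it goes, and it is why the figure is called unsupported rather than wrong. But the plan does not present 1.5% as containing an allowance for differences in response, and nothing in it justifies the implicit limit of about 1.8%.

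On the control comparison, the observed variability is about 10%, where 7 controls suffice. The figure of 92 applies at the extreme of the range, for a two-sided unadjusted test. The planned adjustment could change the residual SD, and the comparison is not among the objectives. All of this is fair. The documents do not allow one to say that the claim fails, only that it cannot be verified above the SD that an unstated number of controls supports. The plan itself chose to assert the range up to 20%.

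The difference in wording between sections 3.1 and 4.6.6 is minor, since cortical regions are brain regions. The figure that might clarify the meaning of 1.16 is not available here.

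**Conclusion.** The concern holds. The longitudinal claim is conditional on an SD of 12-month change of at most about 2.2% with 24 pairs (2.0% with 20), and the documents give no value for that SD in treated MS patients in any of the three primary regions. The detectable change is 0.8% if rescan noise were the whole SD and 6.9% at an assumed SD of 10%. The documents do not say where in that range the study lies.

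The 15% claim holds at the lower end of its SD range with few controls. At the upper end it needs about 92 controls (two-sided) or 45 (one-sided), and neither the number nor the sidedness is stated.

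The study is not shown to be infeasible. At an assumed SD of 5% the detectable change is 3.5%, against the elevation of about 26-29% in cortical lesions quoted in section 4.6.6, although that is a cross-sectional lesion figure. This should be fixed because it changes how a small or null result can be read.

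**What to change.** Restate section 4.6.6 as follows.

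1. **Longitudinal.** State that with 24 complete pairs a paired t-test (two-sided 5%) has 90% power for a mean 12-month change of 0.69 SD of the change (0.76 SD with 20 pairs), and that this SD is not known in treated patients. Add the table of power and detectable change at assumed SDs of 2%, 3%, 5% and 10%. Say that 1.5% applies only if the SD is at most about 2.2% (2.0% with 20 pairs), and that the rescan data, from healthy controls over 3 months, do not include variation in treatment response.
2. **Control comparison.** State the number of healthy controls and the sidedness. Then either limit the 15% claim to the SD that this number supports, or give the power at SD 20%.
3. **Rescan data.** Make sections 3.1 and 4.6.6 agree on the regions covered, and say whether 1.16 is an SD across subjects or across regions.
4. **Clerical.** The affinity split of the rescan controls (2 + 2) does not add to 5.

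The cost is wording and one short table. The stated figures become less favourable, but patients, endpoints and analyses do not change.

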4.7 DATA QUALITY ASSURANCE

Accurate, consistent, and reliable data will be ensured through the use of standard practices and procedures.

5. SAFETY REPORTING OF ADVERSE EVENTS

5.1 ASSESSMENT OF SAFETY

Specification of Safety Variables

Safety assessments will consist of monitoring and reporting adverse events (AEs) and serious adverse events (SAEs) that are considered related to ocrelizumab per standard medical care protocol. This includes all events of death, and any study specific issue of concern.

Adverse Events

An AE is any unfavorable and unintended sign, symptom, or disease temporally associated with the use of an investigational medicinal product (IMP) or other protocol-imposed intervention, regardless of attribution.

This includes the following:

- AEs not previously observed in the subject that emerge during the protocol-specified AE reporting period, including signs or symptoms associated with MS that were not present prior to the AE reporting period.
- Complications that occur as a result of protocol-mandated interventions (e.g., invasive procedures such as radiotracer injection).
- If applicable, AEs that occur prior to assignment of study treatment associated with medication washout, no treatment run-in, or other protocol-mandated intervention.
- Preexisting medical conditions (other than the condition being studied) judged by the investigator to have worsened in severity or frequency or changed in character during the protocol-specified AE reporting period.

Serious Adverse Events

- An AE should be classified as an SAE if the following criteria are met:
- It results in death (i.e., the AE actually causes or leads to death).
- It is life threatening (i.e., the AE, in the view of the investigator, places the subject at immediate risk of death. It does not include an AE that, had it occurred in a more severe form, might have caused death.).
- It requires or prolongs inpatient hospitalization.
- It results in persistent or significant disability/incapacity (i.e., the AE results in substantial disruption of the subject's ability to conduct normal life functions).
- It results in a congenital anomaly/birth defect in a neonate/infant born to a mother exposed to the IMP.
- It is considered a significant medical event by the investigator based on medical judgment (e.g., may jeopardize the subject or may require medical/surgical intervention to prevent one of the outcomes listed above).

Unexpected adverse events are those not listed in the Package Insert (P.I.) or current Investigator Brochure (I.B.) or not identified. This includes adverse events for which the specificity or severity is not consistent with the description in the P.I. or I.B. For example, under this definition, hepatic necrosis would be unexpected if the P.I. or I.B. only referred to elevated hepatic enzymes or hepatitis.

For patients receiving combination therapy, causality will be assessed individually for each protocol-mandated therapy.

5.3 PROCEDURES FOR ELICITING, RECORDING, AND REPORTING ADVERSE EVENTS

Eliciting Adverse Events

A consistent methodology for eliciting AEs at all subject evaluation timepoints should be adopted. Examples of non-directive questions include:

- "How have you felt since your last clinical visit?"
- "Have you had any new/changed health problems since you were last here?"

Specific Instructions for Recording Adverse Events

Investigators should use correct medical terminology/concepts when reporting AEs or SAEs. Avoid colloquialisms and abbreviations.

a. Diagnosis vs. Signs and Symptoms

If known at the time of reporting, a diagnosis should be reported rather than individual signs and symptoms (e.g., record only liver failure or hepatitis rather than jaundice, asterixis, and elevated transaminases). However, if a constellation of signs and/or symptoms cannot be medically characterized as a single diagnosis or syndrome at the time of reporting, it is ok to report the information that is currently available. If a diagnosis is subsequently established, it should be reported as follow-up information.

b. Deaths

All deaths that occur during the protocol-specified AE reporting period (see Section 5.1.2), regardless of attribution, will be reported to the appropriate parties. When recording a death, the event or condition that caused or **Protocol: Ocrelizumab (Institution or Cooperative Group Name)**19/P {Protocol Number}

30032018

contributed to the fatal outcome should be reported as the single medical concept. If the cause of death is unknown and cannot be ascertained at the time of reporting, report "Unexplained Death".

c. Preexisting Medical Conditions

A preexisting medical condition is one that is present at the start of the study. Such conditions should be reported as medical and surgical history. A preexisting medical condition should be re-assessed throughout the trial and reported as an AE or SAE only if the frequency, severity, or character of the condition worsens during the study. When reporting such events, it is important to convey the concept that the preexisting condition has changed by including applicable descriptors (e.g., "more frequent headaches").

d. Hospitalizations for Medical or Surgical Procedures

Any AE that results in hospitalization or prolonged hospitalization should be documented and reported as an SAE. If a subject is hospitalized to undergo a medical or surgical procedure as a result of an AE, the event responsible for the procedure, not the procedure itself, should be reported as the SAE. For example, if a subject is hospitalized to undergo coronary bypass surgery, record the heart condition that necessitated the bypass as the SAE.

Hospitalizations for the following reasons do not require reporting:

- Hospitalization or prolonged hospitalization for diagnostic or elective surgical procedures for preexisting conditions
- Hospitalization or prolonged hospitalization required to allow efficacy measurement for the study or
- Hospitalization or prolonged hospitalization for scheduled therapy of the target disease of the study.

e. Assessment of Severity of Adverse Events

The adverse event severity grading scale for the NCI CTCAE (v5.0) will be used for assessing adverse event severity. Below Table should be used for assessing severity for adverse events that are not specifically listed in the NCI CTCAE.

Adverse Event Severity Grading Scale for Events Not Specifically Listed in NCI CTCAE

Grade Severity

- 1 Mild; asymptomatic or mild symptoms; clinical or diagnostic observations only; or intervention not indicated
- Moderate; minimal, local, or non-invasive intervention indicated; or limiting age appropriate instrumental activities of daily living^a

- 3 Severe or medically significant, but not immediately life threatening; hospitalization or prolongation of hospitalization indicated; disabling; or limiting self care activities of daily living^{b,c}.
- 4 Life-threatening consequences or urgent intervention indicated^d
- 5 Death related to adverse event^d

NCI CTCAE = National Cancer Institute Common Terminology Criteria for Adverse Events.

Note: Based on the most recent version of NCI CTCAE (v5.0), which can be found at: http://ctep.cancer.gov/protocolDevelopment/electronic applications/ctc.htm

- a. Instrumental activities of daily living refer to preparing meals, shopping for groceries or clothes, using the telephone, managing money, etc.
- b. Examples of self-care activities of daily living include bathing, dressing and undressing, feeding oneself, using the toilet, and taking medications, as performed by patients who are not bedridden.
- c. If an event is assessed as a "significant medical event," it must be reported as a serious adverse event
- d. Grade 4 and 5 events must be reported as serious adverse events

f. Pregnancy

If a female subject becomes pregnant while receiving the study drug or within 6 months after the last dose of study drug, or if the female partner of a male study subject becomes pregnant while the study subject is receiving the study drug or within 6 months after the last dose of study drug, a report should be completed and expeditiously submitted to Genentech, Inc. Follow-up to obtain the outcome of the pregnancy should also occur. Abortion, whether accidental, therapeutic, or spontaneous, should always be classified as serious, and expeditiously reported as an SAE. Similarly, any congenital anomaly/birth defect in a child born to a female subject exposed to the study drug should be reported as an SAE.

Additional information on any ocrelizumab-exposed pregnancy and infant will be requested by Genentech/Roche Drug Safety at specific time points (i.e. after having received the initial report, at the end of the second trimester, 2 weeks after the expected date of delivery, and at 3, 6, and 12 months of the infant's life).

g. Post-Study Adverse Events The investigator must report any SAE they might become aware of occurring after a subject has completed or discontinued study participation if attributed to prior ocrelizumab exposure. If the investigator should become aware of the development of cancer or a congenital anomaly in a subsequently conceived offspring of a female subject who participated in the study, this should be reported as an SAE adequately to Genentech drug Safety during follow up period

h. Case Transmission Verification of Single Case Reports

The Sponsor agrees to conduct the Case Transmission verification to ensure that all single case reports have been adequately received by Genentech via The Sponsor emailing Genentech a Quarterly line-listing documenting single case reports sent by The Sponsor to Genentech in the preceding time period.

The periodic line-listing will be exchanged within seven (7) calendar days of the end of the agreed time period. Confirmation of receipt should be received within the time period mutually agreed upon.

If discrepancies are identified, the Sponsor and Genentech will cooperate in resolving the discrepancies. The responsible individuals for each party shall handle the matter on a case-by-case basis until satisfactory resolution. The sponsor shall receive reconciliation guidance documents within the 'Activation Package'.

Following Case Transmission Verification, single case reports which have not been received by Genentech shall be forwarded by The Sponsor to Genentech within five (5) calendar days from request by Genentech.

At the end of the study, a final cumulative Case Transmission Verification report will be sent to Genentech

i. AEs of Special Interest (AESIs)

AESIs are a subset of Events to Monitor (EtMs) of scientific and medical concern specific to the product, for which ongoing monitoring and rapid communication by the Investigator to the Sponsor is required. Such an event might require further investigation in order to characterize and understand it. Depending on the nature of the event, rapid communication by the trial Sponsor to other parties (e.g., Regulatory Authorities) may also be warranted.

There are no ocrelizumab Events of Special Interest.

Adverse events of special interest for this study may include the following:

- Cases of potential drug-induced liver injury that include an elevated ALT or AST in combination with either an elevated bilirubin or clinical jaundice, as defined by Hy's law:
 - Treatment-emergent ALT or AST > 3 x ULN in combination with total bilirubin > 2 x ULN
 - Treatment-emergent ALT or AST > 3 x ULN in combination with clinical jaundice
- Data related to a suspected transmission of an infectious agent by the study drug (STIAMP), as defined below:
 - Any organism, virus, or infectious particle (e.g., prion protein transmitting transmissible spongiform encephalopathy), pathogenic or non-pathogenic, is considered an infectious agent. A

transmission of an infectious agent may be suspected from clinical symptoms or laboratory findings that indicate an infection in a patient exposed to a medicinal product. This term applies only when a contamination of the study drug is suspected

j. Exchange OF SINGLE CASE REPORTS

The Sponsor will be responsible for collecting all protocol-defined Adverse Events (AEs)/Serious Adverse Events (SAEs), AEs of Special Interest (AESIs), Special Situation Reports (including pregnancy reports) and Product Complaints (with or without an AE) originating from the Study for the Product.

Investigators must report all the above mentioned single case reports adequately to Genentech within the timelines described below. The completed MedWatch or CIOMS I form or Genentech approved reporting forms should be faxed/emailed immediately upon completion to Genentech at the following contacts:

All protocol-defined AEs, SAEs, AESIs, Special Situation Reports (including pregnancy reports) and Product Complaints with an AE should be sent to:

[contact]

Email: [contact]

All Product Complaints without an AE should be reported to:

PC [contact]

It is understood and agreed that the Sponsor will be responsible for the evaluation of AEs/SAEs, AESIs, Special Situation Reports (including pregnancy reports) and Product Complaints (with or without an AE) originating from the study.

These single case reports will be exchanged between the parties as outlined below so that regulatory obligations are met.

Serious adverse events (SAEs), AEs of Special Interest (AESIs), pregnancy reports (including pregnancy occurring in the partner of a male study subject), other Special Situation Reports and Product Complaints (with or without an AE), where the patient has been exposed to the Genentech Product, will be sent on a MedWatch form or CIOMS I form or on Genentech approved reporting forms to Genentech Drug Safety. Transmission of these reports (initial and follow-up) will be either electronically or by fax and within the timelines specified below:

SADRs

Serious AE reports that are related to the Product shall be transmitted to Genentech within fifteen (15) calendar days of the awareness date.

Other SAEs

Serious AE reports that are unrelated to the Product shall be transmitted to Genentech within thirty (30) calendar days of the awareness date.

Protocol: Ocrelizumab (Institution or Cooperative Group Name) 23/P {Protocol Number}

AESIs

AESIs shall be forwarded to Genentech within fifteen (15) calendar days of the awareness date.

Special Situation Reports

Pregnancy reports

While such reports are not serious AEs or Adverse Drug Reactions (ADRs) per se, as defined herein, any reports of pregnancy (including pregnancy occurring in the partner of a male study subject), where the fetus may have been exposed to the Product, shall be transmitted to Genentech within thirty (30) calendar days of the awareness date. Pregnancies will be followed up until the outcome of the pregnancy is known, whenever possible, based upon due diligence taken to obtain the follow-up information.

Other Special Situation Reports

In addition to all SAEs, pregnancy reports and AESIs, the following other Special Situations Reports should be collected even in the absence of an Adverse Event and transmitted to Genentech within thirty (30) calendar days:

- Data related to the Product usage during breastfeeding
- Data related to overdose, abuse, misuse or medication error (including potentially exposed or intercepted medication errors)
- In addition, reasonable attempts should be made to obtain and submit the age or age group of the patient, in order to be able to identify potential safety signals specific to a particular population

Product Complaints

All Product Complaints (with or without an AE) shall be forwarded to Genentech within fifteen (15) calendar days of the awareness date.

A Product Complaint is defined as any written or oral information received from a complainant that alleges deficiencies related to identity, quality, safety, strength, purity, reliability, durability, effectiveness, or performance of a product after it has been released and distributed to the commercial market or clinical trial.

MEDWATCH 3500A REPORTING GUIDELINES

In addition to completing appropriate patient demographic (Section A) and suspect medication information (Section C & D), the report should include the following information within the Event Description (Section B.5) of the MedWatch 3500A form:

- Protocol number and title description
- Description of event, severity, treatment, and outcome if known
- Supportive laboratory results and diagnostics (Section B.6)

• Investigator's assessment of the relationship of the adverse event to each investigational product and suspect medication

Follow-Up Information

- Additional information may be added to a previously submitted report by any of the following methods:
- Adding to the original MedWatch 3500A report and submitting it as followup
- Adding supplemental summary information and submitting it as follow-up with the original MedWatch 3500A form
- Summarizing new information and faxing it with a cover letter including
 patient identifiers (i.e. D.O.B. initial, patient number), protocol description
 and number, if assigned, brief adverse event description, and notation that
 additional or follow-up information is being submitted (The patient
 identifiers are important so that the new information is added to the correct
 initial report)

MedWatch 3500A (Mandatory Reporting) form is available at https://www.fda.gov/media/69876/download

Reporting to Regulatory Authorities, Ethics Committees and Investigators

[name] as the Sponsor of the Study, will be responsible for the expedited reporting of safety reports originating from the study to the European Medicine Agency (EMA) through Eudravigilance Clinical Trial Module (EVCTM), where applicable.

[name] as the Sponsor of the Study, will be responsible for the preparation of six-monthly Suspected Unexpected Serious Adverse Reaction (SUSAR) reports and their submission to Investigators, Regulatory Authorities and the Institutional Review Board/Independent Ethics Committee (IRB/IEC), where applicable

[name], as the PI of the Study, will be responsible for the expedited reporting of safety reports originating from the Study to the Regulatory Authorities (FDA) where it has been filed an IND in compliance with local regulations.

The Sponsor will be responsible for the expedited reporting of safety reports originating from the Study to the Ethics Committees and Institutional Review Boards (IRB), where applicable.

The Sponsor will be responsible for the distribution of safety information to its own investigators, where relevant, in accordance with local regulations.

Additional Reporting Requirements for IND Holders (if applicable):

For Investigator-Initiated IND Studies, some additional reporting requirements for the FDA apply in accordance with the guidance set forth in 21 CFR § 600.80.

Events meeting the following criteria need to be submitted to the Food and Drug Administration (FDA) as expedited IND Safety Reports according to the following quidance and timelines:

7 Calendar Day Telephone or Fax Report:

The Investigator is required to notify the FDA of any fatal or life-threatening adverse event that is unexpected and assessed by the Investigator to be possibly related to the use of ocrelizumab. An unexpected adverse event is one that is not already described in the ocrelizumab Investigator Brochure. Such reports are to be telephoned or faxed to the FDA and Genentech/Roche within 7 calendar days of first learning of the event.

15 Calendar Day Written Report

The Investigator is also required to notify the FDA and all participating investigators, in a written IND Safety Report, of any serious, unexpected AE that is considered reasonably or possibly related to the use of ocrelizumab. An unexpected adverse event is one that is not already described in the ocrelizumab investigator brochure.

Written IND Safety reports should include an Analysis of Similar Events in accordance with regulation 21 CFR

§ 312.32. All safety reports previously filed by the investigator with the IND concerning similar events should be analyzed and the significance of the new report in light of the previous, similar reports commented on.

Written IND safety reports with Analysis of Similar Events are to be submitted to the FDA, Genentech/Roche, and all participating investigators within 15 calendar days of first learning of the event. The FDA prefers these reports on a MedWatch 3500 form, but alternative formats are acceptable (e.g., summary letter).

FDA fax number for IND Safety Reports:

Fax: [name]

All written IND Safety Reports submitted to the FDA by the Investigator must also be faxed to Genentech/Roche Drug Safety:

Protocol: Ocrelizumab (Institution or Cooperative Group Name) 26/P {Protocol Number}

[contact] or [contact]

And The Sponsor will be responsible for the distribution of safety information to Site IRB:

[contact] [contact]

For questions related to safety reporting, please contact Genentech/Roche Drug Safety:

[contact]

[contact] or [contact]

AGGREGATE REPORTS

IND ANNUAL REPORTS

All IND annual reports submitted to the FDA by the Sponsor-Investigator should be copied to Genentech

Copies of such reports should be emailed to Genentech at: Genentech Drug Safety CTV mail box: [contact]

Other Reports

The Sponsor will forward a copy of the Final Study Report to Genentech/Roche upon completion of the Study.

Study Close-Out

